9.3.3. Observation for First SGT-53 Infusion

For the first infusion of SGT-53, subjects will be monitored and observed for 23 hours from the time of admittance to the clinic. Subjects will receive the infusion in the

outpatient clinic and be monitored there until infusion is completed and for 2 to 8 hours after the completion of the infusion. After the initial period of 2-8 hours, the patient will be admitted and monitored as an inpatient for the remainder of the 23 hour observation period. Alternatively, patients can be admitted directly to the hospital prior to receiving the first infusion of SGT-53 and to be monitored and observed there for, at least, 24 hours from the time of admittance.

Additionally a 12-lead ECG will be performed 2 hours and 23 hours after the first infusion of SGT-53.

During the observation period, subjects will have continued i.v. access with maintenance of a 20 gauge catheter for rapid fluid management if necessary. The IV access rate should be ≥ 100 mL/hour during the observation period.

The patient will continue to receive i.v. fluid at ≥ 100 mL/hr during the observation period after the initial infusion and vital signs (blood pressure, pulse, temperature and respiration) will be obtained every 15 + 5 minutes during infusion, every 30 + 5 minutes for the first two hours after the infusion and every 1 hour \pm 15 minutes during hours 3 to 8 post-infusion, and thereafter every 2 hours \pm 15 minutes for the remainder of the observation period. Patients will be monitored closely for wheezing, change in blood pressure or signs of hypoperfusion such as cold, clammy skin, cyanosis or tachycardia.

Four hours after completion of the first infusion of SGT-53, subjects will receive acetaminophen, 650 mg p.o. The patient will receive acetaminophen 650 mg po alternating with Indocin 25 mg, or an equivalent NSAID, po every 4 hours during the observation period.

During the hospitalization, Demerol 12.5 mg i.v.p.b. must be available as needed for rigors. Epinephrine (1:1000 0.3-0.5 mL s.q. or i.m.) or epinephrine [(1:10,000) 3-5 mL i.v.] must also be IMMEDIATELY available, along with dexamethasone 20 mg i.v. for prn use for suspected acute hypersensitivity reactions, including hypotension or bronchospasm. Insulin will be available for use for subjects with elevation in blood glucose levels.

The next day the subjects will be discharged if medically stable. If at the end of the observation period, the subject has not resolved any SGT-53 related toxicities to \leq grade 1, the subject will be observed until the time at which the managing physician deems the patient medically stable for discharge.

If patient is receiving a second course of treatment, the 23 or 24hour observation period and 12-lead ECG are not required.

9.3.4. Outpatient Clinic for Subsequent SGT-53 Infusions

For subsequent infusions, subjects will be infused with SGT-53 in the outpatient infusion unit of in one of the outpatient ambulatory treatment centers at the clinical trial sites. The treatment centers are staffed with medical personnel and equipment to treat emergency and non-emergency events and is highly experienced with phase I and II trials. Subjects

will be monitored for two hours, as in Section 9.3.1., and will be discharged only if medically stable. The subject can be monitored for up to 8 hours in the clinic prior to discharged if medically stable. If necessary, the subject can be admitted for 23 hour observation as described for the first infusion (Section 9.3.3.).

9.4. Study drug discontinuation and study withdrawal:

Every reasonable effort should be made to maintain patient compliance and participation in the study. However, all patients are free to withdraw from participation in this study at any time, for any reason, and without prejudice.

A patient will be considered as withdrawn from the study if, and only if, he/she withdraws consent, or is lost to follow-up after unsuccessful attempts by the investigator to contact the patient.

The Investigator may terminate a patient from the study for administrative reasons, or in the investigator's opinion, to protect the patient's best interest. Reasons may include the following:

- Patient withdraws consent and refuses to continue procedures/observations.
- If at any time, continued participation in the study is determined not to be in the best interest of the patient.
- Development of a severe (grade 4) or intolerable adverse event that does not resolve within a 14 day time-frame.
- Development of a significant intercurrent illness.
- Deterioration in patient's disease status such that chemotherapy is no longer indicated.
- Termination of the study by the Sponsor. Patient's care will not be affected in the event of premature termination of this study.
- At any time during study in patients with Progressive Disease as defined below, as determined by Investigator (see Section 18.2.)

If a patient is withdrawn before completing the study, the reason for withdrawal will be entered on the appropriate CRF. Whenever possible and reasonable, the evaluations that were to be conducted at the completion of the study and radiographic tumor measurement should be performed at the time of premature discontinuation.

For grade 2 events of increased bilirubin, AST, ALT, dyspnea, or DIC, the dose of SGT-53 can be held for up to two weeks. If the grade 2 event resolves within two weeks, then infusion of SGT-53 can resume at the same dose per calendar at incident week + 1-2 weeks (i.e., treatment would be made up and moved 1-2 weeks later).

For non-hematological events other than increased bilirubin, AST, ALT, dyspnea, or DIC, participants who develop a > or = to grade 2 toxicity (except for alopecia, or fever, chills, hypotension that respond to treatment) or grade 3 fatigue will discontinue twice-

weekly infusions until the toxicity level reduces to at least grade 1. Infusions will be held for one week intervals, and infusions that are withheld will be made-up (i.e. moved 1-2 weeks later). If the toxicity does not resolve within two weeks, study drug will be discontinued.

In the event that a patient is removed from the study for reasons other than toxicity, they can be replaced at the same dose level.

Patients who go off-treatment after receiving any infusions of SGT-53 will be considered eligible for evaluation of toxicity. Patients withdrawing consent prior to initiation of therapy will be replaced at the same dose level.

9.4.1. Patient follow up after study discontinuation:

All patients who received treatment with SGT-53 must be followed-up for 30 days after discontinuation of study drug. The 30-day follow-up visit should include a physical examination, vital signs, concomitant medications and assessment of AEs/SAEs and Urine analysis. Blood samples will be taken for: Hematology (CBC with differential, platelet count), Chemistries (BUN, Cr, Na⁺, K⁺, CO₂, Cl, Mg⁺⁺, Ca⁺⁺, phosphorus, albumin, alkaline phosphatase, ALT, AST, total bilirubin, total protein, glucose, LDH), PT/PTT, and D-dimer. Patients who permanently discontinue study drug(s) for reasons other than complete response, progression, or death should also have visits approximately every 2 months for the first year that should include a MRI, physical examination, vital signs, and recording of concomitant medications for glioblastoma.

Patients who are withdrawn from study treatment due to a complete response will have the 30-day follow-up visit as described above. Further follow-up visits every 2 months will include only a physical/neurological exam, concomitant medications, vital signs and a MRI.

A telephone contact to check on vital status and any additional treatment for glioblastoma will occur at yearly.

9.5. Replacement policy

Patient replacement will be decided by the Safety Monitoring Committee.

9.6. **Dose Modification**

Reduction/interruption of dosing for adverse events may take place at any time. Below are guidelines for dose modification for drug-related toxicities as well as guidelines for their management. These parameters are only a guide and are not intended to supersede the clinical judgment of the treating physician. All adjustments should be made in consultation with the Medical Monitor and the Sponsor.

All dose modifications should be based on the worst preceding toxicity. If study treatment is being held due to toxicity, scheduled visits and all assessments should continue to occur except the dosing of the study drug.

9.7. **Dose Modification Plans:**

9.7.1. SGT-53 and/or Temozolomide

Table 9.7.1. reviews management of **non-hematologic** toxicities as they pertain to both study agents SGT-53 and/or Temozolomide.

Toxicity	Grade 1	Grade 2	Grade 3	Grade 4
Hyperbilirubin-	Continue both	Hold both until	Discontinue	Discontinue
emia	at same dose	grade 1 or less	TMZ, hold	TMZ, hold
Ciliu		in 2 weeks	SGT-53 until	SGT-53
		in 2 woods	grade 1 or less	until grade 1
			(up to 2	or less (up to
			weeks)*	2 weeks)*
AST &/or ALT	Continue both	Hold both until	Discontinue	Discontinue
	at same dose	grade 1 or less	TMZ, hold	TMZ, hold
		in 2 weeks	SGT-53 until	SGT-53
			grade 1 or less	until grade 1
			(up to 2	or less (up to
			weeks)*	2 weeks)*
Dyspnea not	Continue both	Hold both until	Discontinue	Discontinue
associated with	at same dose	grade 1 or less	TMZ, hold	TMZ, hold
infusion		in 2 weeks	SGT-53 until	SGT-53
			grade 1 or less	until grade 1
			(up to 2	or less (up to
			weeks)*	2 weeks)*
DIC	Continue both	Hold both until	Discontinue	Discontinue
	at same dose	grade 1 or less	TMZ, hold	TMZ, hold
		in 2 weeks	SGT-53 until	SGT-53
			grade 1 or less	until grade 1
			(up to 2	or less (up to
			weeks)*	2 weeks)*
Fatigue	Continue both	Continue both	Hold both until	Discontinue
	at same dose	at same dose	grade 1 or less	both
			in 2 weeks	
Infusion	May	May		
reaction	rechallenge	rechallenge		
	after 1 st event,	after 1 st event,	Discontinue inciting agent**	
	if resolves in 2	if resolves in 2		
	h**	h**		
Hypotension	See Section	See Section	See Section 9.3.2	•
during infusion	9.3.2.	9.3.2.		

Other non-	Continue both	Hold both until	Hold both until	Discontinue
hemetoxicity***	at same dose	grade 1 or less	grade 1 or less	both
		in 2 weeks	in 2 weeks	

^{*}If toxicity reduces to grade 1 or less in 2 weeks, patient may continue SGT-53 until end of cycle at discretion of investigator.

***Other non-heme toxicity refers to any non-heme toxicity at least possibly related to SGT-53, or temozolomide with the exception of alopecia, inadequately treated nausea, vomiting, diarrhea, or fever, chills or hypotension which respond promptly to treatment and lasts less than 24 hours.

For grade 2 events of increased bilirubin, AST, ALT, dyspnea, or DIC, the dose of SGT-53 and Temozolomide can be held for up to two weeks. If the grade 2 event reduces at least to grade 1 within two weeks, then infusion of SGT-53 and Temozolomide can resume at the same dose per calendar at incident week + 1-2 weeks (i.e., treatment would be made up and moved 1-2 weeks later).

For non-hematological events other than increased bilirubin, AST, ALT, dyspnea, or DIC, participants who develop a > or = grade 2 toxicity (except for alopecia, fever, chills or hypotension that respond to treatment) or grade 3 fatigue will discontinue twice-weekly infusions until the toxicity level reduces to at least grade 1. Infusions will be held for one week intervals, and infusions that are withheld will be made-up (i.e. moved 1-2 weeks later). If the toxicity does not resolve within two weeks, study drug will be discontinued.

A minimum of 2-week rest period will be required if there is grade III or greater non-hematologic toxicity related to SGT-53/Temozolomide that cannot be controlled with supportive medications/measures. After the minimum 2-week rest period and the toxicity has resolved to a grade II or better, the patient will resume taking the drug at a reduced dose level as shown in Table 9.7.2b below.

Subjects who receive less than four of twelve of the intended drug infusions, due to experiencing these grade 2 events that have not resolved as described above, and that are determined by the PI to be at least probably related to SGT-53, will be considered to have experienced a DLT.

Patients forced to discontinue temozolomide due to a temozolomide-related toxicity (e.g., grade 3, 4 hypersensitivity) will be removed from the study.

^{**}Note that infusion reactions are discussed in detail in Section 9.3.2.

9.7.2. Temozolomide

Table 9.7.2a. reviews management of hematologic toxicities associated with Temozolomide treatment. Note that there are no dose adjustments for anemia.

	Grade 1	Grade 2	Grade 3 or Grade 4
Neutropenia	< LLN to	<1500 to	Grade 3: <1000 to 500/mm ³
	$1500/\text{mm}^3$	$1000/\text{mm}^3$	Grade 4: <500/mm ³
			If resolves to grade ≤ 2 within 14
	Proceed at	Proceed at	days, rechallenge at same dose of
	current dose	current dose	SGT-53, and reduce dose of TMZ
			in increments after each event
			according to Table 9.7.2b below,
			i.e. in Cycle 1reduce to 100
			mg/m ² after the first event, in
			Cycle 2 reduce to 150 mg/m2
			after the first event, if recurs
			reduce to 100 mg/m ² etc
			If recurs at lowest dose of TMZ
			(100 mg/m ² or less), withdraw
			from study. If at any time it does
			not resolve within 14 days,
Tr1 1	ZUNA	<75 000 to	withdraw from study.
Thrombo-	<lln td="" to<=""><75,000 to	Grade 3: <50,000 to 25,000/mm³	</lln>	<75,000 to	Grade 3: <50,000 to 25,000/mm ³
cytopenia	$75,000/\text{mm}^3$	50,000/mm ³	Grade 4: <25,000/mm ³
	Proceed at	Proceed at	If resolves to grade ≤ 2 within 14 days, rechallenge at same dose of
	current dose	current dose	SGT-53, and reduce dose of TMZ
	current dosc	current dosc	in increments after each event
			according to Table 9.7.2b below,
			i.e.in Cycle 1 reduce to 100
			mg/m^2 after the first event, in
			Cycle 2 reduce to 150 mg/m ² after
			the first event, if recurs reduce to
			100 mg/m ² etc
			If recurs at lowest dose of TMZ
			(100 mg/m ² or less), withdraw
			` '
			not resolve within 14 days,
			withdraw from study.
			(100 mg/m ² or less), withdraw from study. If at any time it does not resolve within 14 days,

Table 9.7.2.b Dose de-escalation for TMZ:

Treatment Cycle	Agent	Schedule	Level	Level	Level
			0 (Target Dose)	-1	-2
Cycle 1	TMZ	Days 9-13	150 mg/m^2	100mg/m^2	
Cycle 2 onwards		Days 9-13	200 mg/m ²	150 mg/m ²	100 mg/m^2

In the event of grade III or higher toxicity associated with TMZ after cycle 1, treatment will be interrupted and patient monitored for resolution of toxicity, with subsequent reinitiation of treatment. TMZ dosing will resume after complete resolution of toxicities to Grade II or less.

The dose of Temozolomide will only be escalated to 200 mg/m2 if the patient meets the following criteria: If the CTC nonhematologic toxicity for Cycle 1 is \leq Grade 2 (except for alopecia, nausea, and vomiting, diarrhea, or fever, chills or hypotension which respond promptly to treatment and lasts less than 24 hours), absolute neutrophil count (ANC) is \geq 1,500/mm³, and the platelet count is \geq 100,000/mm³. The dose remains at 200 mg/m2 per day for the first 5 days of each subsequent cycle except if toxicity occurs. If the dose was not escalated at Cycle 2, escalation should not be done in subsequent cycles.

If more than a 2 week delay is required to meet hematologic parameters for treatment, the patient must be removed from study and replaced.

9.7.3. Dose de-escalation for SGT-53:

Permitted dose modifications for SGT-53

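### After related, uncontrolled grade 3–4 non-hematologic toxicity, Section 9.7.1 gives opposite temozolomide instructions for 10 of 12 table cells, and no text ranks them

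*Combined protocol and SAP*

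**What the plan says.** Section 9.7.1 opens by giving Table 9.7.1 charge of non-hematologic "toxicities as they pertain to both study agents SGT-53 and/or Temozolomide".

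- **Table, grades 3 and 4.** For bilirubin, AST/ALT, non-infusion dyspnea and DIC, TMZ is discontinued and SGT-53 is held. For fatigue and other non-hematologic toxicity, both drugs are held at grade 3 and both are discontinued at grade 4.
- **Footnote to the four named toxicities.** It provides for SGT-53 only: "If toxicity reduces to grade 1 or less in 2 weeks, patient may continue SGT-53 until end of cycle", at the investigator's discretion.
- **Rest-period paragraph, same section.** A rest of at least 2 weeks is required "if there is grade III or greater non-hematologic toxicity related to SGT-53/Temozolomide that cannot be controlled with supportive medications/measures". Once that time has passed and the event is down to grade 2 or lower, the instruction is that "the patient will resume taking the drug at a reduced dose level as shown in Table 9.7.2b below". Table 9.7.2b is the TMZ de-escalation table and contains no other drug.
- **Second paragraph after the table.** For events other than the four named toxicities, at grade 2 or above (or grade 3 fatigue), infusions stop until grade 1. Study drug is discontinued if the event has not resolved within two weeks.
- **Removal sentence, end of the section.** Patients forced off TMZ by a TMZ-related toxicity leave the study.

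Section 9.6 calls all of this guidance that does not override clinical judgment, and adds: "All adjustments should be made in consultation with the Medical Monitor and the Sponsor".

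**The concern.** Take a patient with related grade 3 hyperbilirubinemia or DIC that supportive care could not control. The table says discontinue TMZ. Once the event has fallen to grade 2 and two weeks have passed, the paragraph says the patient will resume TMZ at a lower dose. Following either instruction breaches the other.

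The paragraph is triggered only by events that supportive measures cannot control. If it were read as a specific exception to the table, a grade 4 liver event that responded to supportive care would end TMZ, while one that did not respond would lead to a TMZ restart. That ordering is hard to defend as a safety rule. Different investigators, or the two sites, could also act differently on the same event.

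**Working it through.** No power or error-rate figure is involved. The check is a count of table cells, a dose comparison and a search for a text that ranks the two rules.

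**1. Cells in conflict.** Table 9.7.1 has 8 toxicity rows. Leave out infusion reaction and hypotension during infusion, which Section 9.3.2 handles.

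- Rows × grades: 6 × 2 = 12 cells.
- TMZ discontinued, SGT-53 held: 4 rows × 2 grades = 8.
- Both discontinued: grade 4 fatigue and grade 4 other = 2.
- TMZ discontinued in total: 8 + 2 = 10 (4 at grade 3, 6 at grade 4).
- Both held: grade 3 fatigue and grade 3 other = 2. Check: 10 + 2 = 12.

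**2. TMZ dose after the event in the 10 cells.** Table 9.7.2b reduces 150 to 100 mg/m² in cycle 1, and 200 to 150 to 100 mg/m² from cycle 2. Dosing is on days 9–13, which is 5 days.

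- Rest-period paragraph: 100 × 5 = 500 or 150 × 5 = 750 mg/m² per cycle.
- Table 9.7.1, with discontinuation read as lasting: 0 mg/m².

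**3. The two hold cells.** Here both rules can lead to a restart, on different terms.

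| | Table 9.7.1 | Rest-period paragraph |
|---|---|---|
| Time off drug | within 2 weeks | at least 2 weeks |
| Recovery needed | grade 1 or less | grade 2 or better |
| Resumed dose | no reduction stated | reduced TMZ level |

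The time limits meet only at day 14. The second paragraph after the table adds that an event unresolved within two weeks ends study drug, which is when the rest-period paragraph first allows a restart.

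**4. Does any other text rank the rules?**

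- *Removal sentence, Section 9.7.1.* Read with the table, it sends a TMZ-related event in a discontinue cell to study removal, not to a restart. It does not say which rule decides that a patient is forced off TMZ. It also conflicts with the footnote, which lets SGT-53 go on after TMZ has stopped.
- *Section 9.6.* "All dose modifications should be based on the worst preceding toxicity" does not separate the rules, since both are keyed to the worst grade. The guidance status and the consultation requirement set no precedence.
- *Section 9.4.* It lists as a possible reason for termination: "Development of a severe (grade 4) or intolerable adverse event that does not resolve within a 14 day time-frame". The investigator may act on it but need not.
- *Section 9.7.3.* It points investigators to Table 9.7.1 for modifying SGT-53 only.
- *Section 9.7.2.* It has TMZ resume at grade 2 or less after grade 3 or higher TMZ toxicity beyond cycle 1. The section concerns hematologic toxicity, but the sentence is not limited to it.

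None of these settles the TMZ rule.

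**The case against.** The strongest counter-argument is that the section can be read as consistent. The removal sentence takes TMZ-related events in the discontinue cells out of the study, so the rest-period paragraph would apply only to patients whom the table does not discontinue. This has weight: it favours the table for TMZ-related events, and a reader who inferred that nothing in the protocol bears on the conflict would be wrong. It is not conclusive, for the reason in step 4. The reading also leaves the words about toxicity above grade 3 with no application in the six rows, because every grade 4 cell there discontinues TMZ.

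Three stronger readings are tempting and should be resisted.

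- *That the table expressly stops TMZ for good.* It says discontinue, not permanently discontinue. The protocol elsewhere uses the word for temporary stops (infusions in Section 9.3.2 and in the second paragraph after the table) and adds the word permanently in Section 9.3.2 where it means that. A lasting stop is an inference. The contrast between hold and discontinue within the same cells, and a footnote that restarts SGT-53 alone, support it well.
- *That the plan forces an unsafe restart.* Section 9.6 leaves room for clinical judgment and requires consultation with the Medical Monitor and the Sponsor. That makes a forced restart unlikely. Those consulted would still face two opposite instructions.
- *That 10 of 12 measures risk to patients.* It counts table cells. The paragraph covers only related events that supportive measures cannot control.

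**Conclusion.** The inconsistency is real and should be corrected; confidence is moderate. Its scope is drug-related, uncontrolled grade 3–4 non-hematologic toxicity falling in the 10 cells, with a lesser mismatch of time, recovery grade and dose in the other 2. The conclusion rests on two inferences: that discontinue in the table means no restart, and that the drug in the rest-period paragraph is TMZ, which follows from its pointer to a TMZ-only table. The documents give no event rates from which the number of affected patients could be worked out. The matter is one of patient safety and consistent conduct.

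**What to change.** Which rule prevails is a clinical choice for the sponsor; the recommendation takes the safer direction.

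1. State that Table 9.7.1 governs non-hematologic toxicity for both agents.
2. Limit the rest-period paragraph to TMZ dose reduction (Table 9.7.2b) after grade 3 fatigue or other grade 3 events that recover to grade 1 or less within 2 weeks. State that TMZ is not rechallenged where the table says discontinue.
3. Limit the second paragraph after the table to grades 2–3 (grade 3 for fatigue), so that it no longer conflicts with stopping both drugs at grade 4. Make the same edit in Section 9.4, which repeats that text.
4. Reconcile the removal sentence with the footnote: say whether a patient taken off TMZ under the table may finish the cycle of SGT-53 or leaves the study.
5. Limit the grade 2 restart sentence in Section 9.7.2 to hematologic toxicity.

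The cost is a text-only amendment to a few sentences in Sections 9.4, 9.7.1 and 9.7.2, with no added visits, procedures or patients.
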